### **Study Day 1**

Day 1 is defined as the first day that IP is administered to the subject. For subjects who are randomized but not dosed after randomization, the Study Day 1 is defined as the date of randomization. The day before Day 1 is referenced as Day -1.

### **Study Day**

- On or after Study Day 1: Study Day = (Study Date - Date of Study Day 1) + 1
- Before Study Day 1: Study Day = (Study Date - Date of Study Day 1)

#### **5.4 Study Time Interval**

##### **5.4.1 Study Periods**

The following data will be categorized into treatment periods, if applicable. Any data occurred after EOS date will not be included in the analysis [REDACTED]

Study Phase	Start Time Point	End Time Point
Initial Treatment Phase	Study Day 1	
For Treatment-emergent Adverse Event:
 

• Min (First OEP Dose Date – 1, EOS date) for subjects who received OEP dose;

• EOS Date, for subjects who did not receive any OEP dose

 
For lab, ECG, [REDACTED], Neurological Evaluation and Vital Signs:
 

• Min (First OEP Dose Date, EOS date) for subjects who received OEP dose;

• EOS Date, for subjects who did not receive any OEP dose

 
[REDACTED]

Study Phase	Start Time Point	End Time Point
Optional Extension Phase	For Treatment-emergent Adverse Event: • First OEP Dose Date For [REDACTED] lab, ECG, [REDACTED] Neurological Evaluation and Vital Signs: • First OEP Dose Date + 1	For Treatment-emergent Adverse Event, lab, ECG, [REDACTED] Neurological Evaluation and Vital Signs: • EOS Date
Entire Study	Study day 1	EOS

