### 3.5 Estimated Study Duration

#### 3.5.1 Study Duration for Subjects

The estimated study duration for subjects completing only the initial 12 week treatment phase is up to 27 weeks, and includes:

- Up to 3 weeks for screening
- 12 week treatment phase
- 12 week safety follow-up phase (16 weeks after the last dose of AMG 334)

The estimated study duration for subjects completing the initial 12 week treatment phase and the optional 40-week extension phase is up to 67 weeks, and includes

- Up to 3 weeks for screening
- 12 week treatment phase
- Optional 40-week extension phase
- 12 week safety follow-up phase (16 weeks after the last dose of AMG 334)

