## 7.2.17 Optional 40-Week Extension Phase

The following procedures will be completed during the optional 40-week extension phase, for adolescents who choose to continue treatment, at the times designated in the Schedule of Activities ([Table 1](#) and [Table 2](#)). All visits during this phase are  $\pm$  4 days of the scheduled time point. Children 6 to < 12 years of age will not be offered the option to enter the optional 40-week extension phase.

- Confirmation that the Informed Consent Form [Appendix A](#) has been signed
- Body weight (pre-dose)
- Vital signs (eg, blood pressure, heart rate, temperature) (pre-dose)
- Physical examination (pre-dose)
- Laboratory Assessments:
  - Chemistry Panel
  - Hematology Panel
  - Urinalysis
  - Urine Pregnancy Test pre-dose (female subjects of reproductive potential)
- Serious Adverse Event reporting
- Adverse Event reporting

- Adverse Device Effect reporting
- Documentation of concomitant and headache rescue medications
- AMG 334 serum PK Sample (pre-dose)

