### **3. Study Overview**

#### **3.1 Study Design**

This is a Phase 1b, multicenter, randomized, open-label, multiple-dose study evaluating AMG 334 in male and female children (6 to < 12 years of age) and adolescents (12 to < 18 years of age) with migraine. The study population will consist of 2 cohorts based on body weight at baseline enrolling a total of at least **52** subjects and up to approximately 60 subjects in the study.

Cohort 1 will enroll at least **12** subjects and up to approximately 22 subjects in total with body weight of < 40 kg. At least **9** subjects in Cohort 1 must be aged 6 to < 12 years old including at least **2** subjects aged 6 to < 10 years old, at the time of consent.

Cohort 2 will enroll at least 35 subjects and up to approximately 38 subjects in total with a body weight of  $\geq$  40 kg at baseline. It is anticipated that most subjects in this cohort will be 12 to < 18 years of age. Enrollment requirements for subjects in Cohort 1 and Cohort 2 will be tracked and administered via Interactive Voice Response System (IVRS) to ensure that the minimum number of subjects in each cohort is achieved. Enrollment will be staggered by age category with adolescents (ie, subjects 12 to < 18 years of age) starting enrollment first.

Children 6 to < 12 years of age at the time of consent will participate in the initial treatment phase, for a total of 12 weeks of treatment. Adolescents 12 to < 18 years of age at the time of consent will participate in the initial treatment phase for a total of 12 weeks of treatment after which they will have the option of continuing treatment in an optional 40-week extension phase, for a total of 52 weeks of treatment. A safety follow-up visit will take place 16 weeks after the last dose to complete end of study (EOS) assessments either (i) after completion of the initial 12-week treatment phase, (ii) after completion of the optional 40-week extension phase for those adolescents who choose

---

to continue treatment or (iii) after the last dose received before discontinuation of treatment during the study.

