### 3.2 Sample Size

The study population will consist of 2 cohorts based on body weight enrolling a total of at least **52** subjects up to approximately 60 subjects in the study. Cohort 1 will enroll at least **12** subjects and up to approximately 22 subjects in total with body weight of < 40 kg at baseline. It is anticipated that most subjects in this cohort will be 6 to < 12 years of age. Cohort 2 will enrol at least 35 subjects and up to approximately 38 subjects with a body weight of  $\geq$  40 kg at baseline. It is anticipated that most subjects in this cohort will be 12 to < 18 years of age.

Subjects weighing < 40 kg (Cohort 1) will receive a dose of 35 mg or 70 mg for a total of at least **12** and up to approximately **15** subjects completing Week 12 assessments.

Subjects weighing  $\geq$  40 kg (Cohort 2) will receive a dose of 70 mg or 140 mg for a total of at least 26 and up to approximately 30 subjects completing Week 12 assessments.

The rate of early discontinuation up to Week 12 assessments is assumed to be 20% and similar across the two cohorts.

All subjects in this study will be administered AMG 334. The sample size for this study is based on clinical and practical considerations to adequately fulfil its objectives and to inform on planned phase 3 pediatric studies. Assuming clearance (CL) and central volume of distribution (Vc) on body weight basis is similar between pediatric subjects and adults, and assuming the percentage coefficient of variation for CL and Vc are 43% and 53%, respectively (based on total between-subject-variability from adult population PK), the proposed sample size provides > 80% power to estimate 95% confidence interval (CI) of CL and Vc within 60-140% of the true parameters for both weight cohorts combined and across the two age categories ([Wang Y et al, 2012](#)).

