### Duration of IP Exposure During ITP

If subject enters into OEP,

Minimum (Last ITP IP Dose Date + 27, First OEP Dose Date - 1, EOS Date) – First ITP IP Dose Date + 1

Otherwise,

Minimum (Last ITP IP Dose Date + 27, EOS Date) – First ITP IP Dose Date + 1

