### Subject Incidence

The subject incidence for a given event in a given period is defined as the number of subjects with at least one reported occurrence of the event divided by the number of subjects who enter that period (ie, number of at-risk subjects). For subjects with multiple occurrences of the same event in a given period, the event will only be counted once per subject in that period.

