## 7.2 Primary Analysis

**The primary analysis for the study will be performed at the End of the Study milestone described in the protocol Section 3.5.2. All data will be cleaned and a database lock will occur.**

No formal hypothesis testing will be performed; all analyses will be descriptive. PK and safety data will include summaries by body weight cohort and AMG 334 treatment dosage group. **Primary analysis will include safety summaries for ITP only. Safety data will be analyzed by GBS and PK data will be analyzed by CPMS.** The review of the results of this primary analysis will inform on further pediatric studies utilizing AMG 334.

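### Initial-phase adverse events are counted to about Day 84 for extension entrants but to about Day 169 for everyone else, so the primary safety table compares weight cohorts and age groups over unequal windows

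*SAP*

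**What the plan says.** SAP 5.4.1 defines the ITP for TEAEs by two rules. A subject who receives an extension dose leaves the ITP the day before that dose (or at end of study, if earlier). For the others the period ends at "EOS Date, for subjects who did not receive any OEP dose". For laboratory, ECG, neurological and vital-sign data the rule is the same, except that an entrant's ITP includes the day of the first extension dose.

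Other passages determine who falls under which rule, and where it matters:

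- Protocol 7.2.17: "Children 6 to < 12 years of age will not be offered the option to enter the optional 40-week extension phase".
- SAP 3.2, on Cohort 1 (< 40 kg): "It is anticipated that most subjects in this cohort will be 6 to < 12 years of age". SAP 3.1 sets a minimum of 9 such children. Cohort 2 is expected to be mostly adolescents.
- SAP 7.2: "Primary analysis will include safety summaries for ITP only", summarised by weight cohort and dose. SAP 9.1 adds age-group safety summaries where appropriate.
- SAP 5.6: subject incidence is the number of subjects with an event "divided by the number of subjects who enter that period". The exposure-adjusted rate, also planned in SAP 9.6.2, uses the whole period as time at risk for subjects without the event.
- SAP 5.6, duration of ITP exposure for non-entrants, runs to "Minimum (Last ITP IP Dose Date + 27, EOS Date"), so it stops 27 days after the last ITP dose at the latest.
- Protocol 3.5.1 lists a "12 week safety follow-up phase (16 weeks after the last dose of AMG 334") as a separate item from the 12-week treatment phase.

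**The concern.** TEAE incidence is a primary endpoint, and SAP 7.2 says the primary results will inform further pediatric studies. Under one ITP label, the table would count some subjects for 12 weeks on treatment and others for 12 weeks on treatment plus 12 weeks of follow-up. Which subjects get the long window is not random. Every child does, and so does every adolescent who declines the extension or stops early. A reader comparing the two cohort columns, or children with adolescents, would see a difference produced partly by the counting rule.

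The 35 mg dose exists only in Cohort 1 and the 140 mg dose only in Cohort 2, so those dose columns inherit the imbalance. They are already confounded with weight and age; this adds one more difference, and an avoidable one. Worst-post-baseline laboratory shifts are also affected, because they use all assessments and so take in Day 169 values for non-entrants only. By-visit laboratory and vital-sign summaries are largely unaffected.

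**Working it through.** **Windows, from the documents.** ITP doses are on Days 1, 29 and 57 (Protocol 6.2.1.1). The first extension dose is at Week 12, Day 85 (Protocol Table 2). End of study is 16 weeks after the last dose.

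- End of study without extension: 57 + 16 × 7 = Day 169, which reproduces Protocol 7.2.18. With extension: 337 + 112 = Day 449, also as stated.
- Entrant's TEAE window: 85 − 1 = Day 84.
- Non-entrant's window: Day 169 after three doses, Day 141 (29 + 112) after two, Day 113 (1 + 112) after one.
- Ratio for three-dose subjects: 169 / 84 = 2.01.
- ITP exposure under SAP 5.6: (57 + 27) − 1 + 1 = 84 days for entrants and three-dose non-entrants alike.

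**Effect on crude incidence.** The documents do not give extension uptake *u* among adolescents, the shares of children *c1* and *c2* in Cohorts 1 and 2, or the TEAE rate. They set only a floor for *c1* (9/22 = 41% to 9/12 = 75%) and the word most. I assume 30% incidence by Day 84 and the same hazard in every group.

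- Incidence by Day 169, constant hazard: 1 − 0.70^(169/84) = 0.512. With the hazard halved after Day 84: 0.416.
- Share of a cohort with the short window: s = (1 − c) × u. Mean window: 169 − 85s.
- Cohort incidence: 0.30s + 0.512(1 − s).
- Gap, Cohort 1 minus Cohort 2: (0.512 − 0.300) × u × (c1 − c2) = 0.212 × u × (c1 − c2).

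| u; c1 / c2 | s, Cohort 1 / 2 | Mean window, days (ratio) | Incidence, Cohort 1 / 2 | Gap, constant hazard | Gap, hazard halved |
|---|---|---|---|---|---|
| 50%; 55% / 40% | 0.225 / 0.300 | 149.9 / 143.5 (1.04) | 46.4% / 44.8% | 1.6 points | 0.9 |
| 50%; 75% / 15% | 0.125 / 0.425 | 158.4 / 132.9 (1.19) | 48.6% / 42.2% | 6.4 points | 3.5 |
| 90%; 100% / 0% | 0 / 0.900 | 169 / 92.5 (1.83) | 51.2% / 32.1% | 19.1 points | 10.4 |

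The gap is 0 if u = 0 or if no events occur after Day 84. If 20% discontinue early in both cohorts, as the plan assumes, the split applies to the other 80% and the constant-hazard gaps become 1.3, 5.1 and 15.3.

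For children against adolescents, c1 = 1 and c2 = 0, so the constant-hazard gap is 21.2 × u points: 0, 10.6 and 19.1 at u = 0, 50% and 90%.

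**Effect on the exposure-adjusted rate.** The rate is incidence divided by expected time to first event or end of period. With λ = −ln(0.70)/84 = 0.00425 per day, expected time is 0.30/λ = 70.7 days in the short window. In the long window it is 120.6 days (constant hazard), 125.1 (halved) or 70.7 + 0.70 × 85 = 130.2 (no later events). Weighting by s gives these Cohort 1 / Cohort 2 rate ratios in the three scenarios:

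- constant hazard: 1.00 in all three;
- halved after Day 84: 0.99, 0.94, 0.81;
- no events after Day 84: 0.96, 0.85, 0.59.

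**The case against.** The strongest reply is that the remedy is already planned. SAP 9.6.2 reports an exposure-adjusted rate beside the crude one, with events and time at risk taken over the same period. Under a constant hazard that rate is undistorted, and if no events follow Day 84 the crude proportion is undistorted. Between those limits, however, both are distorted, in opposite directions, and a reader cannot tell which to trust. The effective half-life is 28 days (Protocol 2.2.3), so the added 85 days span about three half-lives without further dosing, and a falling drug-related hazard is plausible.

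Second, carrying follow-up events into the last treatment phase is a defensible convention. TEAEs are defined up to end of study, adverse events are collected through follow-up, the extension period also runs to end of study, and drug is still present early in follow-up. Duration of exposure is a different quantity from an event-counting window. All of this stands: the SAP does not contradict itself here. The convention still makes the columns of the primary table non-comparable.

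Third, everything is descriptive, age-group tables are conditional, the cohorts are not randomised against each other, and the gap may be small. The gaps of 1.6 and 6.4 points are about 0.2 to 1.4 subjects in a Cohort 1 of 12 to 22. The binomial standard error of the cohort difference is about 13 to 17 points (45% incidence; 22 vs 38 or 12 vs 35 subjects). That limits the importance of the point, but does not remove a systematic difference that is cheap to avoid.

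**Conclusion.** The concern holds and should be fixed. The 84- and 169-day windows and their link to age follow from the documents alone. The size of the resulting gap rests on assumed uptake, age mix, event rate and hazard shape. At 30% incidence by Day 84 the cohort gap runs from 0 to 19.1 points. The top value needs 90% uptake, cohorts fully split by age, a constant hazard and no early discontinuation. No error rate changes, because nothing is tested. The randomised dose contrast within a cohort is largely unaffected, provided uptake is similar by dose.

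**What to change.** In SAP 5.4.1, for the primary TEAE summaries, compute subject incidence and the exposure-adjusted rate from Day 1 to min(Study Day 84, First OEP Dose Date − 1, EOS Date) for every subject, where OEP is the optional extension phase. Label it *first 12 weeks (Days 1–84)*. Report later events that precede any extension dose in a separate *after Day 84 / follow-up* column, and keep through-EOS totals under the Entire Study period that SAP 5.4.1 already defines. For worst-post-baseline laboratory shifts and the ECG and neurological summaries, end the ITP at the Week 12 visit for everyone; end-of-study values remain in the Entire Study summaries. The neurological part may change little, since the end-of-study procedure list in Protocol 7.2.18 has no such examination.

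The cost is SAP wording and one derived period variable, with no new data and none discarded. There are three small drawbacks:

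- Non-entrants' follow-up TEAEs leave the main column. For children these are the only later safety observations, so the follow-up column should sit beside it.
- If dose 3 is given on Day 60, exposure under SAP 5.6 runs to Day 87 (60 + 27), and Days 85–87 fall in the follow-up column.
- With the ±4-day extension visit window, an entrant's window can end as early as Day 80, or a few pre-extension days can fall in the follow-up column.

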## 5.5 Subject Disposition

### Randomized

Individuals are considered randomized if they have been assigned a randomization number. Randomized individuals are referred to as “subjects”.

### Exposed to Investigational Product

Subjects are defined as exposed if they receive at least one dose of investigational product.

### Completing the Initial Treatment Phase

Subjects are defined as completing the ITP if they complete the Week 12 assessment. It will be derived from the End of Initial Treatment Phase eCRF with “Completed” as the primary reason for ending study phase.

### Completing the Optional Extension Phase

Subjects are defined as completing the OEP if they complete the Week 52 assessment. It will be derived from the End of Optional Extension Treatment Phase eCRF with “Completed” as the primary reason for ending study phase.

### Completing Study

Subjects are defined as completing study if they complete the entire study **duration, as applicable**. It will be derived from the End of Study eCRF with “Completed” as the primary reason for ending study.

## 5.6 Arithmetic Calculations

### Change from Baseline:

The arithmetic difference between a post-baseline value and the baseline value:

- Change from Baseline = (Post-baseline Value – Baseline Value)
- Percent change from Baseline = [(Post-baseline Value – Baseline Value) / Baseline Value] x 100

### Duration of IP Exposure During ITP

If subject enters into OEP,

Minimum (Last ITP IP Dose Date + 27, First OEP Dose Date - 1, EOS Date) – First ITP IP Dose Date + 1

Otherwise,

Minimum (Last ITP IP Dose Date + 27, EOS Date) – First ITP IP Dose Date + 1

### Duration of IP Exposure During OEP

Minimum (Last OEP IP Dose Date + 27, EOS Date) – First OEP IP Dose Date + 1

### Duration of IP Exposure During Entire Study

Minimum (Last IP Dose Date + 27, EOS Date) – First IP Dose Date + 1

### Subject Incidence

The subject incidence for a given event in a given period is defined as the number of subjects with at least one reported occurrence of the event divided by the number of subjects who enter that period (ie, number of at-risk subjects). For subjects with multiple occurrences of the same event in a given period, the event will only be counted once per subject in that period.

### Exposure-adjusted Incidence Rate

The exposure-adjusted incidence rate for a given event in a given period is defined as the number of subjects with at least one reported occurrence of the event in a given period divided by total exposure time of all subjects who are at risk for the event. For subjects with a given event, only the time until the onset of each subject's first event contributes to the exposure time. For subjects without a given event, the exposure time

is the entire duration of the period. This incidence rate will be presented as number of subjects per 100 subject-years.

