#### 7.2.18 End of Study Visit

All Subjects will be followed for 16 weeks after the last administration of AMG 334.

The following procedures will be completed during the final visit (Study Day 169, early termination or Day 449, if subject continued in the optional 40-week extension phase).

- Physical Examination as per standard of care
- Single 12-Lead ECG
- Height and Weight Measurements
- Vital signs (eg, blood pressure, heart rate, temperature)
- Laboratory Assessments:
  - Chemistry Panel
  - Hematology Panel
  - Urinalysis
  - Urine Pregnancy Test (female subjects of reproductive potential)
  - Drug and Alcohol Screen

- AMG 334 serum PK Sample
- Serious Adverse Event reporting
- Adverse Event reporting
- Adverse Device Effect reporting
- Documentation of concomitant and rescue medications

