## 7.3 Final Analysis

The final analysis will **utilize the same database as the primary analysis.**

No formal hypothesis testing will be performed; all analyses will be descriptive. PK and safety data will include summaries by body weight cohort and AMG 334 treatment dosage group. **Final analysis will include safety summaries for the entire study and separately for OEP only, as appropriate. Safety data will be analyzed by GBS and PK data will be analyzed by CPMS.**

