### 9.6.2 Adverse Events

The Medical Dictionary for Regulatory Activities (MedDRA) version 24.1 or later will be used to code all events categorized as adverse events to a system organ class and a preferred term.

The subject incidence and exposure-adjusted subject incidence of all treatment-emergent adverse events, treatment-emergent serious adverse events, device-related treatment-emergent adverse events, treatment-emergent adverse events leading to discontinuation of **investigational product**, and fatal adverse events **will be summarized**.

Treatment-emergent adverse events, treatment-emergent serious adverse events, device-related treatment-emergent adverse events, treatment-emergent adverse events leading to discontinuation of AMG 334, and fatal adverse events will be tabulated by system organ class (SOC) in alphabetical order and preferred term (PT) in descending order of frequency. Summaries of treatment-emergent AEs and treatment-emergent serious adverse events will be tabulated by system organ class, preferred term, and

grade. The severity of each AE will be graded using Common Terminology Criteria for AE (CTCAE) version 4.03 criteria.

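### The exposure-adjusted rate for adverse events leading to discontinuation of investigational product counts follow-up time when a subject who has finished dosing is no longer at risk, so it is too low, and unequally so between groups

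*SAP*

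**What the plan says.** SAP 5.6 (Exposure-adjusted Incidence Rate) divides the number of subjects with the event by the total exposure time of subjects at risk for it. For a subject who has the event, "only the time until the onset of each subject's first event contributes to the exposure time". For a subject who does not, the exposure time "is the entire duration of the period. This incidence rate will be presented as number of subjects per 100 subject-years".

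SAP 5.4.1 fixes the periods. The extension phase and the entire study end at the end-of-study (EOS) date. For adverse events, the initial phase ends at "EOS Date, for subjects who did not receive any OEP dose". For those who did receive an extension dose it ends at the earlier of two dates, in a rule that begins "Min (First OEP Dose Date – 1". EOS includes the safety follow-up: "All Subjects will be followed for 16 weeks after the last administration of AMG 334" (Protocol 7.2.18).

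SAP 9.6.2 applies the rate to five classes: all treatment-emergent events, serious events, "device-related treatment-emergent adverse events, treatment-emergent adverse events leading to discontinuation of" investigational product (IP), and fatal events. No class has its own risk window. The scope includes later summaries: "Final analysis will include safety summaries for the entire study and separately for OEP only, as appropriate" (SAP 7.3).

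The same SAP section also defines a duration of IP exposure for each period. For the entire study it is "Minimum (Last IP Dose Date + 27, EOS Date) – First IP Dose Date + 1". The rate does not use it.

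**The concern.** A rate per subject-year is meaningful when the denominator is time in which the event could have been observed. An adverse event can lead to discontinuation of IP only while dosing is still in progress or still due. A subject who has completed dosing contributes the remaining follow-up to the denominator but can add nothing to the numerator. This departs from the SAP's own restriction of the denominator to subjects at risk: that wording selects subjects, but the sentences after it give them the whole period.

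The dilution differs between groups. Children are not offered the extension (Protocol 7.2.17), so follow-up is about half of their study time. For an adolescent who extends it is about a fifth. If the discontinuation rate is read across age groups, or across weight cohorts that differ in age mix, the group with the shorter treatment will look better tolerated than it was.

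**Working it through.** **Inputs.** Doses are on Days 1, 29 and 57 (Protocol 6.2.1.1). Extension doses run from Day 85 to Day 337 (Protocol Table 2). Follow-up is 16 weeks = 112 days. EOS is Day 169 or Day 449 (Protocol 7.2.18). The IP-exposure rule ends at last dose + 27 days (SAP 5.6). Visit windows and early dropouts are ignored.

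**Plan's own timeline.** 57 + 112 = 169 and 337 + 112 = 449, so both EOS days are reproduced. The documents state no exposure-adjusted rate to reproduce.

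**Days per event-free completer.**

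| Group and period | Period in the rate | Duration of IP exposure | Ratio |
|---|---|---|---|
| Child or non-extending adolescent, initial phase = entire study | 169 | 57 + 27 − 1 + 1 = 84 | 84/169 = 0.50 |
| Extension adolescent, entire study | 449 | 337 + 27 − 1 + 1 = 364 | 364/449 = 0.81 |
| Extension adolescent, extension phase | 449 − 85 + 1 = 365 | 337 + 27 − 85 + 1 = 280 | 280/365 = 0.77 |
| Extension adolescent, initial phase | 84 | 84 | 84/84 = 1.00 |

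**Effect on the rate.** Let a constant hazard h act only during IP exposure T within a period P. The planned rate then estimates

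[1 − exp(−hT)] / {[1 − exp(−hT)]/h + exp(−hT)(P − T)},

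which is close to h × T/P when events are few. With h = 10 per 100 subject-years (assumed), it gives 5.0 for children and 8.2 for extension adolescents over the entire study. For h from 5 to 40 per 100 subject-years, the share of the true rate is 0.50 to 0.51 and 0.82 to 0.84, so the result hardly depends on h.

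**Child:adolescent ratio under equal hazards, entire study.** Extension uptake is not given in the documents.
- 100% uptake: (84/169)/(364/449) = 0.497/0.811 = 0.61.
- 50% uptake: mean adolescent exposure is (364 + 84)/2 = 224 days and mean period (449 + 169)/2 = 309 days. The share is 224/309 = 0.725, and 0.497/0.725 = 0.69.
- 0% uptake: the ratio is 1, but both rates are half the true rate.

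**Same ratio, initial phase.** At 100% uptake it is 0.497/1.00 = 0.50. At 50% uptake the mean adolescent period is (84 + 169)/2 = 126.5 days, the share is 84/126.5 = 0.664, and the ratio is 0.497/0.664 = 0.75.

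**Example.** One discontinuation event on Day 29 among 12 subjects, the other 11 completing:
- Children, as planned: 100 × 365.25/(11 × 169 + 29) = 19.3 per 100 subject-years. On IP exposure: 100 × 365.25/(11 × 84 + 29) = 38.3.
- Extension adolescents, as planned: 100 × 365.25/(11 × 449 + 29) = 7.4. On IP exposure: 100 × 365.25/(11 × 364 + 29) = 9.1.

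**The case against.** The strongest reply is that the rule suits most of what it is applied to. Treatment-emergent events are counted up to EOS (SAP 5.1), so numerator and denominator match for all, serious and fatal events. The stated effective half-life is 28 days (Protocol 2.2.3), so 16 weeks covers four half-lives and is not clearly drug-free time. This stands. A reader might infer that all the exposure-adjusted rates are wrong, but the documents do not support that.

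Nor do they support extending the point to device-related events. Those are defined by a causality flag, not by timing (SAP 5.1), and are collected through the safety follow-up (Protocol 9.2.2.2).

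The two definitions in SAP 5.6 might also be read as contradicting each other. They do not: duration of IP exposure has its own output (SAP 9.6.8), and nothing designates it as the adverse-event denominator. It is simply a better-fitting variable, already derived, for this one class.

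A reader might put the end of risk at the last planned dose, which gives 57/169 = 0.34 and 337/449 = 0.75. I do not take these as the size. Protocol 6.2.1.1 provides for permanent discontinuation throughout the 12-week phase, and an adolescent may still be due a dose on Day 85.

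Finally, it is tempting to say that the entire-study rate would give false reassurance for the Phase 3 paediatric studies. SAP 7.3 gives the final analysis no such purpose. Main tables are by weight cohort and dose, with age-group summaries only where appropriate (SAP 9.1). Crude incidence and reasons for discontinuation are also reported (SAP 9.6.2 and 9.2).

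None of this answers the narrow point: for events leading to discontinuation of IP, the stated denominator includes time not at risk.

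**Conclusion.** The point holds for one of the five event classes, treatment-emergent adverse events leading to discontinuation of IP. Measured against the SAP's own exposure window, the planned rate is about 50% too low for children and non-extending adolescents. For extension adolescents it is about 19% too low over the entire study and 23% too low in the extension phase. Equal on-treatment hazards would appear as an entire-study child:adolescent ratio of about 0.61 to 0.69 for extension uptake of 100% to 50%.

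These figures assume scheduled visit days, completers, a hazard confined to the exposure window, and the stated uptakes. The practical weight is modest because the summaries are descriptive, no hypothesis is tested, and crude incidence stands beside the rate.

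**What to change.** In SAP 5.6, for treatment-emergent adverse events leading to discontinuation of IP only, set the exposure time of event-free subjects to their duration of IP exposure for the period being summarised. Subjects with the event keep time to first onset. Leave the whole-period denominator for all, serious, fatal and device-related events, and state in a footnote which denominator each rate uses.

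The cost is a sentence of SAP text and a change of denominator in one set of tables, from variables already defined and with no new data. The reported discontinuation rates will be higher. The remedy is also not exact: after the final planned dose it still counts up to 27 days per subject in which no further dose is due. If risk is held to end at the last planned dose, that leaves 57/84 = 0.68 of the true rate in children and 337/364 = 0.93 in extension adolescents. The footnote should say so.
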